9.4.3.2. Comorbidities

The following comorbidities will be identified based on the presence of at least one ICD-9-CM/ICD-10-CM diagnosis code or NDC/HCPCS codes identified using all available data during the baseline period and are operationalized in Table 4.

Table 4. Operationalization of comorbidities			
History or presence of upper gastrointestinal anatomic or motor disorders	Operationalization: ICD-10-CM code	Operationalization: ICD- 9-CM code	
Esophageal strictures, webs, diverticula, or other gastroduodenal pathology seen on esophagogastroduodenoscop y	K22.2 Esophageal obstruction K57 Diverticular disease of intestine K22.5 Diverticulum of esophagus, acquired K31.5 Obstruction of duodenum Q39.3 Congenital stenosis and stricture of esophagus Q39.4 Esophageal web	530.3 Stricture and stenosis of esophagus 537.3 Other obstruction of duodenum 530.6 Diverticulum of esophagus, acquired 562 Diverticula of intestine 750.3 Congenital tracheoesophageal fistula, esophageal atresia and stenosis	
Gastrointestinal strictures of any kind	K56.69x Other intestinal obstruction K50 Crohn's Disease	555 Regional enteritis 560.9 Unspecified intestinal obstruction, Enterostenosis; of intestine or colon: obstruction, occlusion, stenosis, stricture.	
Esophageal or gastric motor disorders (eg, scleroderma)	C15 Malignant neoplasm of esophagus Z85.01 Personal history of malignant neoplasm of esophagus K31.84 Gastroparesis K91.1 Postgastric surgery	150 Malignant neoplasm of esophagus 530 Diseases of esophagus 787.1 Heartburn V10.03 Personal history of malignant neoplasm of esophagus	

		T
	syndromes K20 Esophagitis K21 Gastro-esophageal reflux disease K22 Other diseases of esophagus R12 Heartburn K30 Functional dyspepsia K23 Disorders of esophagus in diseases classified elsewhere Q39 Congenital malformations of esophagus	536.3 Gastroparesis 564.2 Postgastric surgery syndromes 750.3 Congenital tracheoesophageal fistula, esophageal atresia and stenosis 750.4 Other specified congenital anomalies of esophagus 536.8 Dyspepsia and other specified disorders of function of stomach
Barrett's esophagus	K22.7x Barrett's esophagus	530.85 Barrett's esophagus
Peptic ulcer disease, erosive gastritis and/or erosive duodenitis	K25 Gastric ulcer K26 Duodenal ulcer K27.x Peptic ulcer, site unspecified K28 Gastrojejunal ulcer	531 Gastric ulcer 532 Duodenal ulcer 533 Peptic ulcer site unspecified 534 Gastrojejunal ulcer

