Eosinophilic esophagitis by histology (eosinophils per high powered field)	K20.0 Eosinophilic esophagitis	530.13 Eosinophilic esophagitis
Gastrointestinal malabsorption	K90 Intestinal malabsorption	579 Intestinal malabsorption
H. pylori infection within the past 6 months	B96.81 Helicobacter pylori [H. pylori] as the cause of diseases classified elsewhere	041.86 Helicobacter pylori [H. pylori]

Cystic Fibrosis	E84 Cystic fibrosis	277.0x Cystic fibrosis
	E84.8 Cystic fibrosis with other manifestations	
Diagnosed as having or has received treatment for esophageal, gastric, pyloric channel, or duodenal ulceration		
Proton pump inhibitors	Operationalization: NDC code	Operationalization: HCPCS code
Omeprazole (Prilosec)	70515062501	-
Esomeprazole (Nexium)	00186504054, 00186504005, 00186504031	-
Lansoprazole (Prevacid)	64764054130, 64764054105, 64764054111, 64764054119	-
Rabeprazole (AcipHex)	62856024330	-
Pantoprazole (Protonix) HCPCS Source	00008092351, 00008092355, 00008092360	S0164 Injection, pantoprazole sodium, 40 mg
H2-blockers		
Famotidine (Pepcid AC, Pepcid Oral) HCPCS Source	16837087210, 16837087220, 16837087222, 16837087230, 16837087231,	J3490 Unclassified drugs

Version 2.0, 10 February 2022			
	16837087260, 16837087275, 16837087290		
Cimetidine (Tagamet, Tagamet HB)	63029022201, 63029022202, 63029022203, 63029022204, 63029022205, 63029022270	-	
Ranitidine (Zantac, Zantac 75, Zantac Efferdose, Zantac injection, and Zantac Syrup) HCPCS Source	52565-102, 67751015101(for 150, max strength), 00173036238	J2780 Injection, ranitidine hydrochloride, 25 mg	
Nizatidine Capsules (Axid AR, Axid Capsules, Nizatidine Capsules)	65726-144-15, 65726-145- 10	-	

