9.7. Data management

De-identified Optum EHR data will be analyzed using the Aetion Evidence Platform (AEP). Data to be used for the proposed analysis have already been linked and uploaded into the AEP. The AEP is a data-handling technology, which allows for the analysis of large patient datasets by indexing patient data into a form that can be queried by an internal patient variable language and has been previously used.^{3,4,5} Data are minimally transformed at the point of connection to the AEP, thus the original format of the raw Optum EHR data is preserved. At the point of data connection to the platform some discard rules are applied. Patient events are excluded if patient identification (ID) is missing and if the "start of enrollment" date is preceded by the "end of enrollment" date in the original data. Additionally, patient events are excluded if there are no dates associated with them, or if the start date of the event is preceded by the end date of the event (e.g. discharge date precedes admission date for an inpatient event). Action IDs are assigned to Optum EHR patient IDs and a crosswalk file is kept as a protected file available upon request to authorized parties. The data are at the individual patient level and will be analyzed within the AEP.

9.8. **Data analysis**

090177e1996138d1\Approved\Approved On: 23-Feb-2022 16:44 (GMT)

All statistical analysis will be performed in the two cohorts of interest, ie, infants aged 1 month to < 1 year and patients aged 1 to < 2 years, separately using the AEP version 4.2. Analysis combining the two cohorts of interest will not be performed.

Descriptive statistics will be presented for key variables of interest i.e., demographic characteristics, comorbidities and duration and dose of IV pantoprazole, listed in Section 9.4.3 to characterize the overall cohort treated with IV pantoprazole and in the 3 subgroups defined based on the presence or absence of GERD and EE and listed under Section 9.3.3. These will include counts and percentages for categorical data and statistics such as mean, median, standard deviation, and range for continuous variables.

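### In Table 4 a J3490 (unclassified drugs) record for any drug is enough to flag a child as a baseline famotidine user

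*Protocol*

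**What the plan says.** Section 9.4.3.2 bases each comorbidity variable on the "presence of at least one ICD-9-CM/ICD-10-CM diagnosis code or NDC/HCPCS codes identified using all available data during the baseline period". The code types are joined by *or*.

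Table 4 then lists acid-suppressing drugs beneath the item "Diagnosed as having or has received treatment for esophageal, gastric, pyloric channel, or duodenal ulceration". Under H2-blockers, the row "Famotidine (Pepcid AC, Pepcid Oral) HCPCS Source" gives eight NDCs, beginning "16837087210, 16837087220, 16837087222, 16837087230, 16837087231", and one HCPCS entry, "J3490 Unclassified drugs". The ranitidine row in the same block has "J2780 Injection, ranitidine hydrochloride, 25 mg".

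Section 9.8 states how these variables are used: "Descriptive statistics will be presented for key variables of interest i.e., demographic characteristics, comorbidities and duration and dose of IV pantoprazole". They are summarised for the overall cohort and for the three GERD/EE subgroups, in each age cohort separately.

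**The concern.** A code list should contain only codes that identify the thing being measured. J3490, by the protocol's own label, covers drugs that have no specific classification. A record under it does not show that the child received famotidine.

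What is at stake is the baseline description. Readers will use these rows to judge how far each subgroup had been treated for acid-related disease before IV pantoprazole. If unrelated drugs feed the famotidine flag, that picture is partly wrong. If J3490 billing differs between the GERD and non-GERD subgroups, some of an apparent difference in H2-blocker use would come from billing.

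**Working it through.** The protocol has no figure to reproduce here, so the check is a reading of the rule against the row, then of everything that might limit or spread the effect.

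**1. Is J3490 sufficient alone?** Yes. The rule in Section 9.4.3.2 uses *or*, and neither that section nor Table 4 requires J3490 to sit with an NDC, a drug name or an administration record. J3490 is one of 8 + 1 = 9 codes in the row, so it is not the sole definition of famotidine use, but it is enough without the others.

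**2. Is this the table's general practice?** No.

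| Drug rows in Table 4 | HCPCS entry | Names the drug? |
|---|---|---|
| Pantoprazole | S0164 | Yes |
| Ranitidine | J2780 | Yes |
| Famotidine | J3490 | No |
| Omeprazole, esomeprazole, lansoprazole, rabeprazole, cimetidine, nizatidine | dash | none listed |

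Only famotidine is given a catch-all code.

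**3. Would the planned checks catch it?** Probably not. Section 9.9 has covariate measures built from the protocol's own codes and says the protocol will be followed strictly. Double implementation compares two programs written to the same list, so both would contain J3490.

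**4. Is it a deliberate choice of sensitivity over specificity?** Section 9.10 defends broad algorithms for capturing safety outcomes. That reasoning does not extend to baseline treatment history.

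**5. Where does the flag go?** Into the descriptive tables of Section 9.8. It does not enter eligibility (9.3.1, 9.3.2), the GERD/EE subgroups (9.3.3, Table 1), the outcome definitions (9.4.2, Table 3), or follow-up and incidence rates (9.8).

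**6. Direction and size.** Let *p* be the true proportion with baseline famotidine use, *s* the proportion of those users whom the row captures, and *f* the proportion of non-users with a J3490 record for another drug. Ignoring other errors in the listed NDCs,

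reported proportion = *p·s* + (1 − *p*)·*f*.

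The second term is the false-positive part contributed by J3490, and it cannot be negative. The reported figure exceeds *p* only if (1 − *p*)·*f* > *p*·(1 − *s*). The protocol gives none of *p*, *s* or *f*, so neither the size of the false-positive part nor the sign of the net error can be computed.

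**The case against.** The strongest case on the other side is that nothing the study was set up to estimate depends on this flag. The study has no comparator and no hypotheses, and no adjustment is described. That is correct, and it caps the severity.

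Other objections also stand in part:

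- **The reported item is not fully specified.** The protocol does not say whether famotidine has its own line or only feeds the ulceration item above it. In a composite, a J3490 false positive matters only for a child with no other qualifying drug or diagnosis. The effect on that item is therefore possible, not certain.
- **A pairing rule could sit elsewhere.** Section 9.8 leaves detailed methods to an SAP that is not at hand, and the words *HCPCS Source* in the row may point to a reference that is not shown. Neither corrects the code list that the protocol itself fixes and says will be followed.
- **J3490 may be the row's only route to some true users.** The row is labelled with Pepcid AC and Pepcid Oral, and all eight NDCs share the stem 168370872. This bears on the remedy.

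A reader might infer three stronger claims that the document does not support:

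- *Reported H2-blocker use will be inflated by a stated amount.* There is no input for such a figure, and missed true users could offset the false positives.
- *J3490 charges must be common because these are inpatients.* The reference to inpatient codes in Section 9.4.1 concerns pantoprazole exposure. The comorbidities draw on all available baseline data, and no J3490 frequency is given.
- *Any injectable drug would count.* The descriptor says only that the drugs are unclassified.

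**Conclusion.** Wrong as written, and minor. The famotidine row treats a code that does not identify famotidine as sufficient evidence of its use, and no text in the protocol restricts it. The result is false positives in the baseline famotidine (H2-blocker) variable and possibly in the ulceration diagnosis-or-treatment item, for each cohort and subgroup.

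This rests on reading the *or* in Section 9.4.3.2 literally and on there being no pairing rule outside the protocol. How many children are affected cannot be derived, and a net overstatement is not shown. The incidence rates and the populations they are computed in do not change.

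**What to change.** In the famotidine row of Table 4, count J3490 only when the same record also carries a famotidine NDC or drug name. Section 9.5 says the data include medications prescribed and administered, so a drug name may be available. If the pairing cannot be implemented, remove J3490 from the row.

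Pairing is preferable to plain deletion, because J3490 is the row's only HCPCS code and deletion would also drop famotidine records that can be identified. Matching on drug name goes slightly beyond the NDC and HCPCS lists in Table 4, so it needs a short specification as well as the edit to the cell. The cost is some lost capture of famotidine billed under J3490 with no drug identifier, to an extent the document does not allow to be estimated. No other analysis needs to change.

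### Table 4 ascertains prior use of five acid suppressants through one labeler-product each, and its famotidine, pantoprazole and ranitidine rows are also poorly specified, so the baseline drug-history percentages will be unreliable

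*Protocol*

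**What the plan says.** Protocol section 9.4.3.2 sets the rule for every row of Table 4: a condition or drug is present if there is "presence of at least one ICD-9-CM/ICD-10-CM diagnosis code or NDC/HCPCS codes identified using all available data during the baseline period". One matching code is enough, and without one the child is recorded as not having had the drug.

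The drug rows then list the codes. Esomeprazole has "00186504054, 00186504005, 00186504031" and lansoprazole has "64764054130, 64764054105, 64764054111, 64764054119". Omeprazole and rabeprazole have one NDC each (70515062501 and 62856024330). The cimetidine row, whose label opens "Cimetidine (Tagamet, Tagamet HB", has six NDCs. The HCPCS cell is empty for all five.

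The famotidine row, whose label opens "Famotidine (Pepcid AC, Pepcid Oral", has eight NDCs, the first five being "16837087210, 16837087220, 16837087222, 16837087230, 16837087231", and the HCPCS code J3490, described as unclassified drugs. The pantoprazole row has three NDCs and S0164. The ranitidine row, labelled "Ranitidine (Zantac, Zantac 75, Zantac Efferdose, Zantac injection, and Zantac Syrup", has "52565-102, 67751015101(for 150, max strength), 00173036238" and J2780, described as an injection. Nizatidine has two NDCs and no HCPCS code.

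Section 9.9 says that the measures are built from the codes given in the protocol and that the protocol is to be followed strictly. The lists are therefore the operative definition. Section 9.8 reports these variables as counts and percentages for each overall cohort and its three subgroups.

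**The concern.** An NDC identifies one labeler's product in one package. A list confined to one labeler-product does not find the drug; it finds that product. A child who had the same ingredient from another labeler, or in another strength or form, is counted as never having had it.

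Acid suppressants are the only prior-drug history among the key variables in section 9.4.3. The study has no comparator, so readers rely on the baseline table to judge whether the treated children were already on acid suppression. If some rows under-count, one can over-count and one is nearly empty by construction, that table cannot support such a judgement.

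**Working it through.** The protocol gives no expected prevalence of prior acid-suppressant use, so there is no planned figure to reproduce. The check is a count, followed by a sizing that rests on assumptions.

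**Step 1: how to split the codes.** Table 2 writes the IV pantoprazole codes with hyphens, for example 0008-0923-51. Table 4 writes the same code as 00008092351. The 11 digits therefore split 5-4-2 into labeler, product and package. In Table 2 the last segment changes only with the number of vials.

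**Step 2: distinct labeler-products in Table 4.**

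| Drug | NDC entries | Labeler-products | HCPCS |
|---|---|---|---|
| Omeprazole | 1 | 1 (70515-0625) | none |
| Esomeprazole | 3 | 1 (00186-5040) | none |
| Lansoprazole | 4 | 1 (64764-0541) | none |
| Rabeprazole | 1 | 1 (62856-0243) | none |
| Cimetidine | 6 | 1 (63029-0222) | none |
| Famotidine | 8 | 1 (16837-0872) | J3490 |
| Pantoprazole | 3 | 1 (00008-0923) | S0164 |
| Ranitidine | 3 | 3 (three labelers) | J2780 |
| Nizatidine | 2 | 2 (one labeler) | none |

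The total is 31 NDC entries. The first five rows hold 1 + 3 + 4 + 1 + 6 = 15, all within five labeler-products and with no second route.

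**Step 3: the pantoprazole row against Table 2.** Table 2 uses 12 NDCs across four stems (0008-0941, 0008-2001, 0008-4001, 0008-0923), plus S0164 and C9113, to define IV exposure. All four codes in Table 4's pantoprazole row (three NDCs on stem 0008-0923, and S0164) are among them. Section 9.3.1 makes the first IV administration the index date, and section 9.8 treats baseline as the time before it. An earlier inpatient record with one of these codes would itself set the index date. Only records that do not count as exposure, such as one outside the inpatient setting or before the study period, could fill the row. It contains no code that Table 2 does not label as IV, so it gives no route to oral pantoprazole.

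**Step 4: labels against codes.** The ranitidine label names five products, including a syrup, against three NDC entries and an injection code. The famotidine and cimetidine labels name two products each, over one NDC stem each.

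**Step 5: size, by assumption only.** Let p be true prior use of any acid suppressant, s the share of that use carried by the listed NDCs, and j the share of children flagged through a HCPCS code. Treating the two routes as independent, reported use is

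R = 1 − (1 − p·s)(1 − j).

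With j = 0 this is R = p·s. For p from 20% to 80%:

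- s = 1%: R = 0.2% to 0.8%
- s = 10%: R = 2% to 8%
- s = 50%: R = 10% to 40%

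With HCPCS flags the result changes. For p = 50%, s = 10%, j = 20%: R = 1 − 0.95 × 0.80 = 24%, below the true value. For p = 20%, s = 10%, j = 50%: R = 1 − 0.98 × 0.50 = 51%, above it. None of p, s and j is in the protocol.

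**The case against.** The strongest reply is that these rows are descriptive. They sit in Table 4 under a heading about diagnosed or treated ulceration. No planned analysis stratifies or adjusts by prior acid suppression, and the protocol does not claim that its patients are new to acid suppression. Table 4 enters neither eligibility, nor the GERD and EE subgroups, nor the outcomes, nor person-time. All of this stands, and it limits the point to the baseline table and how it is read. It does not make the percentages right.

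A second reply is that HCPCS codes offer another route. That is true for ranitidine (J2780, drug-specific and not tied to a labeler, but for the injection only), for famotidine (J3490, not specific to it) and for pantoprazole (S0164, which is also an exposure code). It is not true for the five drugs with an empty HCPCS cell. The ranitidine entry without a package segment is not clearly a loss either: matched at product level, it would cover more packages.

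A reader might infer that baseline acid-suppressant use as a whole will be reported as close to zero. The documents do not support that. It would need both a very small share of use under the listed NDCs and almost no HCPCS flags, and the protocol fixes neither. Because J3490 can flag children given other drugs, the class figure could even be too high.

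**Conclusion.** The point holds for the descriptive baseline table. Followed as written, the plan will under-count prior omeprazole, esomeprazole, lansoprazole, rabeprazole and cimetidine, because each is found only through one labeler-product. This assumes only that some use in these children is recorded under other NDCs. The size cannot be determined from the protocol; the ranges in the working are illustrations, not estimates.

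Famotidine may be under-counted through its NDCs and over-counted through J3490, with the net direction unknown. The pantoprazole row will show little or no prior use and no oral use. The ranitidine codes do not clearly cover the products named in the row label.

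The incidence rates of the primary objective and of secondary objective 1 are numerically unaffected. A reader might suspect biased safety rates, but Table 4 does not feed them. The harm is to interpretation: an apparent absence of prior acid suppression could simply reflect the code list.

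**What to change.** Define prior use in Table 4 by active ingredient, across all labelers, strengths, forms and routes, in the prescribed and administered medication records that section 9.5 says the data source holds. Section 9.5 does not describe an ingredient field. If there is none, use a complete NDC list for each ingredient.

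Keep drug-specific HCPCS codes such as J2780, and remove J3490. For pantoprazole, apply the same ingredient rule so that oral products are included, and state that codes shared with Table 2 cannot show earlier IV use that would itself set the index date. Make the row labels match what the definition covers.

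The cost is a little programming and a revised table. Cohorts, follow-up and incidence analyses do not change.

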9.4.3.3. Duration and dose of IV Pantoprazole

Duration of IV pantoprazole in days will be ascertained as follows: Date of last infusion during the observation period – date of first infusion during the observation period plus 1 day (minus treatment gaps, defined as a date with no record of infusion between the date of last infusion and date of first infusion; up to 7 days treatment gap between infusions will be allowed). Total daily dose of IV pantoprazole will be reported in mg/kg/day.

9.5. Data sources

The Optum EHR with Integrated Claims dataset from the US contains electronic health records data with prescriptions, diagnoses, and provider information as well as practice management data and claims information for deterministically-matched patients. The population of the dataset is made up of commercial health plan members and Medicare Advantage members, across all 50 states. The database currently encompasses the claims and EHR data of more than 95 million patients with approximately 1.9 million patients aged less than 2 years from 01 January 2007 through 31 December 2020. This dataset contains a combination of structured data (e.g. diagnoses, procedures, prescriptions) and information from unstructured data (e.g. drug rationale, provider notes) from the electronic health record and corresponding claims information for those instances. The claims are verified,

adjudicated, and adjusted by the relevant insurer, and de-identified by Optum prior to providing access to the database. Patients are only included in the database if they had both medical and prescription drug coverage, as well as the EHR information. Information is processed, normalized, and standardized across the continuum of care from both acute inpatient stays and outpatient visits. Optum® data elements include demographics, medications prescribed and administered, immunizations, allergies, lab results (including microbiology), vital signs and other observable measurements, clinical and inpatient stay administrative data and coded diagnoses and procedures.¹

9.6. Study size

There are no a priori hypotheses specified, and therefore, sample size calculations are not applicable. All eligible patients meeting inclusion/exclusion criteria will be included in the study. Based on preliminary feasibility, it is anticipated that 7,489 infants aged 1 month to <1 year and 6,657 patients aged 1 to <2 years who have been treated with IV pantoprazole will be eligible for inclusion in the study. Table 5 below shows the 95% confidence intervals around varying hypothetical frequencies of outcomes given a 7,489 and 6,657 patient sample, calculated using the Wilson score interval.

Table 5. Precision estimates for varying frequencies of outcomes for given 7,489 and 6,657 patient samples

Sample size	Outcome Frequency	N Events*	Lower 95% Bound	Upper 95% Bound
7489	0.002	15	0.0012	0.0033
	0.005	37	0.0036	0.0068
	0.01	75	0.0080	0.0125
	0.05	374	0.0452	0.0551
	0.1	749	0.0934	0.1070
	0.2	1498	0.1911	0.2092
6657	0.002	13	0.0011	0.0033
	0.005	33	0.0035	0.0070
	0.01	67	0.0079	0.0128
	0.05	333	0.0450	0.0555

10 February 2022

0.1	666	0.0931	0.1075
0.2	1331	0.1905	0.2097

^{*}Note: Event counts are rounded to nearest whole number

